2. SYNOPSIS OF STUDY DESIGN AND PROCEDURES

Title	PROphylactic ThErapy in Care homes Trial
Acronym	PROTECT-CH
Short title	PROTECT-CH
Chief Investigator	[name]
Research Question	In residents in a UK care home setting (P), which drug or antibody interventions (I) when compared to standard care (C) are effective, safe and cost-effective (O) as prophylaxis for COVID-19?
Objectives	Primary objective
	To provide reliable estimates of the effect of trial treatments for each pairwise comparison with the standard care arm on SARS-CoV-2 infection, morbidity and mortality 60 days after randomisation (or appropriate point dependent on the intervention – where this differs to 60 days further detail will be provided in the specific investigational medicinal product (IMP) Appendix).
	Secondary objectives To assess the effects of trial treatments on mortality (all-cause and cause-specific), admission to hospital (all-cause and cause-specific), healthcare referrals for COVID-19, infection (asymptomatic, symptomatic), time to symptomatic infection and safety through serious adverse reactions. To assess the effects of trial treatments on transmission of SARS-CoV-2 infection.
	Tertiary objectives To assess the cost-effectiveness of trial treatments and explain the contextual factors which influence trial processes including adherence to intervention and outcome measurement regimens, and which might impact on subsequent implementations of pre- or post-exposure prophylaxis for COVID-19 in care homes.
Trial Configuration	Overarching platform trial designed to provide reliable evidence on the efficacy of candidate therapies for preventing SARS-CoV-2 infection and transmission in care homes.
Setting	UK Care homes (residential, nursing, mixed).
Sample size estimate per comparison of an active treatment with standard care	In order to detect an odds ratio of 0.67, a sample size of 200 care homes per principal comparison (around 6,400 residents) is required assuming 1:1 randomisation, two-sided significance level 5%, power 90%, 4-level ordinal primary outcome (no infection proportion 60%, infection remain in CH 15%, admission to hospital all-causes 10%, all-cause mortality 15%), intra-cluster correlation 0.11, coefficient of variation for care home size 0.49, average

	number of residents per care home in trial 32, design effect/inflation factor 5.25.				
Number of participants	Each comparison of an active treatment with standard care requires 200 care homes i.e. in the region of a total of 6,400 residents.				
Eligibility criteria	 Care Home criteria Inclusions Location: UK care homes for older people, with and without nursing. Size: ≥20 beds in the care home in total. Exclusions Care Quality Commission quality: Inadequate, or equivalent in devolved administrations. Care Home criteria at treatment phase Exclusions: Positive PCR or lateral flow test (or equivalent) for SARS-CoV-2 in any resident and/or staff within previous 4 weeks 				
	 Resident criteria at trial entry Inclusions Resident in a Care Home. Age ≥65 years Able to give informed consent for participation or a personal legal representative has been identified who can give consent if resident lacks capacity. 				
	 Exclusions: Identified by care home staff to have entered end-stage palliative care. Resident in care home for short-term respite care. Resident's general practitioner is unable to support their involvement in the trial. 				
	 Resident criteria at treatment phase Exclusions: Currently taking all of the trial interventions. Contraindication to all trial interventions - see IMP appendix. In treatment phase of another COVID-19 prevention or treatment trial 				
Description of interventions	Intervention: To be identified by NIHR Prophylaxis Oversight Group (POG) plus standard care. Each intervention will be described within a separate IMP Appendix, each of which will be updated upon confirmation of use within the trial.				
	Comparator: Standard care, i.e., no additional intervention.				

Randomisation and	 The unit of randomisation is the care home, not the (individual) resident.
blinding	Allocation concealment will be ensured by enrolling care homes and residents prior to revealing the allocation. There will be no blinding apart from the outcomes sourced from routinely collected health data. Where possible IMP interventions will be open-label. Dynamic randomisation will be employed using a probabilistic minimisation algorithm to balance across important baseline characteristics including: Care home type (residential vs nursing vs nursing and residential dual registration) Prior COVID-19 in care home at any time (yes vs no) Size of Care Home - Total number of residents in care home (small (≤30 residents), medium (>30, ≤50 residents), large (>50 residents)) Care home has capacity to give oxygen (yes vs no) Trials of pre-exposure prophylaxis (PFEP, i.e. before the care home has a case) and/or post-exposure prophylaxis (PEP, once the care home has a new case to control an outbreak) will be conducted on the platform. For trials of PrEP, the care home must have had no evidence of SARS-CoV-2 infection for at least 4 weeks. For trials of PEP, care homes will only be randomised once they have an indication of a developing infection, e.g. recent positive PCR or lateral flow test (or equivalent) in a resident or member of staff (index case). The care home must have had no evidence of SARS-CoV-2 infection for at least 4 weeks.
Outcome measures	 Primary endpoint: Four-level ordered categorical scale. Participants will be classified according to the highest level, that is, the most serious event they experience during the 60-day period following randomisation: No SARS-CoV-2 infection. SARS-CoV-2 infection but resident remains in care home. Admission to hospital, all-cause. Death, all-cause. SARS-CoV-2 status (positive or negative) will be diagnosed using PCR or lateral flow testing (or equivalent). A flow chart describing different scenarios of test results depending on which test(s) is (are) performed is presented in Figure A1 (Appendix). Secondary endpoints during the 60 days post-randomisation (unless otherwise stated):

myocardial infarction Electronic frailty index at 60 days Ordinal outcome for the most serious event experienced during the 120 days post-randomisation with the following levels: 1. No SARS-CoV-2 infection, 2. SARS-CoV-2 infection but resident remains in care home, 3. Admission to hospital, all-cause, 4. Death, all-cause. Safety Serious Adverse Reactions (SAR, excluding primary and secondary outcomes) and Suspected Unexpected SARs (SUSARs). Adverse events relevant to the intervention (see relevant IMP-specific Appendix) Clinical – care home level Number of SARS-CoV-2 infections in residents in the care home (aggregate data including residents not participating in PROTECT-CH). Economic evaluation EQ-5D-5L utilities and EQ-VAS at 60 days Quality Adjusted Life Years (QALY) Healthcare resource use and costs Incremental cost-per QALY and Net Monetary Benefit	
homes. The primary approach to between-group comparative analyses will be by intention-to-treat (i.e., according to randomised allocation regardless of adherence to trial allocation). Cluster-level and resident-level descriptive	 home with GP (excluding routine visit), 111, 999 paramedic or Emergency Department assessment, remote hospital consultation. Time to use of dexamethasone in the care home for COVID-19 Time to use of oxygen in the care home for COVID-19 Time to SARS-COV-2 infection - positive PCR or lateral flow test (or equivalent) (i) with symptoms of COVID-19, (ii) without symptoms of COVID-19, (iii) total i.e. either with or without symptoms of COVID-19. Time to first admission to hospital Cause-specific hospital admission Time to death Days alive and not in hospital Cause-specific mortality, including COVID-19, stroke, pulmonary embolism, myocardial infarction Electronic frailty index at 60 days Ordinal outcome for the most serious event experienced during the 120 days post-randomisation with the following levels: 1. No SARS-CoV-2 infection, 2. SARS-CoV-2 infection but resident remains in care home, 3. Admission to hospital, all-cause, 4. Death, all-cause. Safety Serious Adverse Reactions (SAR, excluding primary and secondary outcomes) and Suspected Unexpected SARs (SUSARs). Adverse events relevant to the intervention (see relevant IMP-specific Appendix) Clinical – care home level Number of SARS-CoV-2 infections in residents in the care home (aggregate data including residents not participating in PROTECT-CH). Economic evaluation EQ-5D-5L utilities and EQ-VAS at 60 days Quality Adjusted Life Years (QALY) Healthcare resource use and costs
Primary comparative analyses will employ a multi-level ordinal logistic regression model with a random effect to account for clustering within care homes. The model will adjust for characteristics used in balancing random	homes. The primary approach to between-group comparative analyses will be by intention-to-treat (i.e., according to randomised allocation regardless of adherence to trial allocation). Cluster-level and resident-level descriptive statistics will be used to illustrate balance between the groups at baseline. Primary comparative analyses will employ a multi-level ordinal logistic regression model with a random effect to account for clustering within care

2.1. Sample size and justification

A total of 530 residents per group are required to detect an odds ratio of 0.67 for a 4-level ordinal primary outcome (no infection proportion 60%, infection remain in CH 15%, all-cause hospitalisation 10%, all-cause mortality 15%), assuming a two-sided significance level of 5% and 90% statistical power, with no adjustment for clustering [2].

Care homes of varying size will be included, and the number of residents recruited per care home will likely be in the range 20–60. Assuming an intra-cluster correlation of 0.11, a coefficient of variation for care home size of 0.49 (Lothian population analysis in 189 care homes[3]) and an average of 32 residents per care home in the study (assuming that the average number of beds per care home is 40[4] and that not all residents will take part in the study), this gives rise to a design effect or inflation factor of 5.25[5].

Therefore, to compare a single active treatment versus usual care, we will need in the region of 174 care homes, i.e., in excess of 5,500 residents. Allowing for the uncertainty surrounding the parameters listed above (e.g. levels of mortality and transmission rates are expected to be different in the second wave due to improved preparedness, better treatments and the potential impact of the expected vaccination programme, therefore it is possible that the observed proportions in the control group may differ), we propose a sample size of 200 care homes and a total number of residents in the region of 6,400 per comparison, with sample size re-estimation during the trial (once 60-day outcome data are available for at least 75% of residents randomised to standard care).

Therefore, comparing three active (unrelated) treatments concurrently versus standard care (in a 1:1:1:1 allocation ratio) would require 400 care homes in total, corresponding to around 13,000 residents.

2.2. Blinding and breaking of blind

Care home residents and staff will not be blinded to treatment allocation. Dynamic randomisation of care homes using a minimisation algorithm and release of allocation only following enrolment, resident consent, and baseline data collection, will ensure allocation concealment. The trial statisticians, CI, and members of the TSC will remain blinded prior to treatment codes being revealed (for the final analysis of a comparison). Interim closed reports for the Data Monitoring Committee (DMC) will be prepared by a separate team of statisticians (unblinded to trial intervention) to those that will conduct the final analysis.

2.3. Trial committees

A trial management group (TMG), platform steering committee (PSC) and data monitoring committee (DMC) will be assembled to oversee the trial. The general purpose, responsibilities and structure of the committees are described in the protocol. Further details of the roles and responsibilities of the PSC and DMC can be found in their respective charters agreed prior to the start of recruitment to the trial.

2.4. Outcome measures

Primary and secondary outcomes will be assessed during the 60 days post-randomisation unless stated otherwise. The primary outcome is a four-level ordered categorical outcome. Participants will be classified according to the highest level, that is, the worst, event they experience during the 60-day period following randomisation:

- 1. No SARS-CoV-2 infection.
- 2. SARS-CoV-2 infection but resident remains in care home.
- 3. Admission to hospital, all-cause.
- 4. Death, all-cause.

The outcome measures and their sources are summarised in Error! Reference source not found.

Table 1: Summary of the outcome measures

Outcome measures	Description	Sourc	es	Type of data	Analysis method
		Care Home ascertainment through eCRF	Routine data sources		
Primary outcome					
	Participants will be classified according to the highest level, that is, the most serious event they experience during the 60-day period (or relevant time point) following randomisation:				
A four-level ordinal outcome to	1. No SARS-CoV-2 infection	\checkmark	-		
A four-level ordinal outcome to capture the ability of the drug candidate(s) to prevent/reduce morbidity and mortality from COVID-19 in care home residents, and to reduce transmission in care home settings	 SARS-CoV-2 infection (infection diagnosed with PCR or lateral flow testing (or equivalent)) but resident remains in care home i.e., resident not admitted to hospital. The PCR test results will take primacy if both tests are performed as presented in the flowchart in Section 11.1. Admission to hospital all source 	✓	✓	Ordered categorical	Mixed-effect ordinal logistic regression
	3. Admission to hospital, all-cause	\checkmark	\checkmark		
	4. Death, all-cause	\checkmark	✓	-	
Secondary outcomes	(during the 60 days post-randomisation unless stated otherwise)				
Clinical: individual resident-level					
Healthcare referral for COVID- 19	Healthcare referral for COVID-19 e.g. discussion outside of care home with GP (excluding routine visit), 111 or, 999 paramedic or Emergency Department assessment, remote hospital consultation.	~	~	Time-to- event (first event)	Competing-risks survival regression with cluster– robust standard errors

PROTECT-CH (2033) Statistical Analysis Plan Final version 1.0 02-Aug-2021. Based on protocol version 1.0 Page 12 of 25

Written using WPD 16.5 version 3.0, 13-Sep-2018. Effective date: 13-Oct-2018. Template Author: [name]

Outcome measures	Description	Sourc	ces	Type of data	Analysis method
Participant receives dexamethasone in the care home for COVID-19	Use of dexamethasone in care home for COVID- 19	\checkmark	-	Time-to- event	Competing-risks survival regression with cluster– robust standard errors
Participant receives oxygen in the care home for COVID-19	Use of oxygen in care home for COVID-19 (for care homes with capacity to give oxygen)	\checkmark	-	Time-to- event	Competing-risks survival regression with cluster– robust standard errors
Time to SARS-CoV-2 infection* - positive PCR or lateral flow test (or equivalent) (i) with symptoms of COVID-19 (ii) without symptoms of COVID-19, (iii) Total, i.e., either with or without symptoms of COVID-19.	Time from randomisation to SARS-CoV-2 infection - positive PCR or lateral flow test (or equivalent). The date of the LFT test will be used as the date of event if LFT is positive and confirmed by the PCR test. (i) with symptoms of COVID-19 (ii) without symptoms of COVID-19 (iii) with/without symptoms of COVID-19	✓ (presence/ absence of symptoms)	✓ (PCR test results)	Time-to- event	Competing-risks survival regression with cluster– robust standard errors
Time to first admission to hospital [†]	Time from randomisation to first hospitalisation for any reason	\checkmark	~	Time-to- event	Competing-risks survival regression with cluster– robust standard errors
Cause specific hospital admission		\checkmark	~		Descriptive
Days alive and not in hospital †		-	✓	Continuous	Linear mixed-effect model
Time to death	Time from randomisation to death (all-cause) in days	\checkmark	✓	Time-to- event	Shared frailty model

PROTECT-CH (2033) Statistical Analysis Plan Final version 1.0 02-Aug-2021. Based on protocol version 1.0 Page 13 of 25

Written using WPD 16.5 version 3.0, 13-Sep-2018. Effective date: 13-Oct-2018. Template Author: [name]

Outcome measures	Description	Sourc	es	Type of data	Analysis method
Cause-specific mortality, including COVID-19, stroke, pulmonary embolism, myocardial infarction	COVID-19	~		Binary	Descriptive
	stroke			Binary	Descriptive
	pulmonary embolism		•	Binary	Descriptive
	myocardial infarction			Binary	Descriptive
Electronic frailty index at 60 days	Electronic frailty index (eFI) The eFI is presented as a score (e.g. if 9 deficits are present out of a possible total of 36 the FI score = 0.25) - higher scores indicate increasing frailty. The eFI score is used to define frailty categories: - Fit (0 - 0.12) - Mild frailty (> 0.12 - 0.24) - Moderate frailty (> 0.24 - 0.36) - Severe frailty (> 0.36) A composite endpoint strategy will be used to handle the eFI outcome truncated due to death by adding an extra category for death to ensure that death equates to the worst outcome.	-	✓	Ordered categorical	Mixed-effect ordinal logistic regression
Ordinal outcome for the most serious event experienced during the 120 days post- randomisation	Four-level ordinal outcome: No SARS-CoV-2 infection, SARS-CoV-2 infection but resident remains in care home, Admission to hospital, all- cause and Death, all-cause.	✓	✓	Ordered categorical	Mixed-effect ordinal logistic regression
Clinical: care home level					

Page **14** of **25**

Written using WPD 16.5 version 3.0, 13-Sep-2018. Effective date: 13-Oct-2018. Template Author: [name]

Outcome measures	Description	Sourc	es	Type of data	Analysis method
Number of SARS-CoV-2 infections in residents in the care home	Aggregate infection rate in the care home. The numerator will be all confirmed SARS-CoV-2 infections including residents not participating in PROTECT-CH trial and the denominator will be the number of residents in the care home at randomisation.	✓	~	Rate (Proportion)	Linear regression (rate difference) and Poisson regression (rate ratio)
Additional Safety:					
Serious Adverse Reactions (SAR, excluding primary and secondary outcomes) and Suspected Unexpected SAR (SUSAR)		✓			
Adverse events relevant to the intervention as specified in relevant IMP specific appendix to protocol		✓			

*For PEP- only applicable for residents not positive at randomisation; [†]excludes residents with directive for no hospitalisation

Page **15** of **25**

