13.2. Analysis of Outcome Measures

Statistical analyses

The analysis and reporting of the trial will be in accordance with CONSORT guidelines for adaptive and cluster designs [14, 15] with the primary comparative analyses being conducted according to randomised allocation with due emphasis on confidence intervals for between-arm comparisons. All comparative analyses will be based on contemporaneously randomised care homes. A full statistical analysis plan will be developed and agreed with the Platform Steering Committee (PSC) prior to the first release of treatment allocations for final pairwise comparison. The primary approach to between-group comparative analyses will be by intention-to-treat (i.e. according to randomised allocation regardless of adherence to trial allocation). Cluster-level and resident-level descriptive statistics will be used to illustrate balance between the groups at baseline.

Trial	Prophylactic therapy in care homes trial	Protocol	Final v1.0	date:	13-May-2021	Page:	35 of 44
name:	U1111-1265-4068	version:					

Primary comparative analyses will employ a multi-level ordinal logistic regression model including all residents eligible for the intervention of interest prior to care home randomisation. The model will adjust for the minimisation factors, plus the individual-level covariates age, sex and vaccination status. A random effect to adjust for clustering within care homes will be used. The treatment comparison will be presented as an adjusted common odds ratio for a shift in the direction of a better outcome on the ordinal scale together with 95% confidence intervals.[16-19]

Secondary outcomes will be analysed using appropriate regression models dependent on data type (binary, categorical, continuous, time to event etc.), adjusted similarly and accounting for clustering within care homes.

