7.4. Secondary outcomes

Table 1 lists all the secondary outcomes and the type of variables.

Individual-level secondary outcomes will be analysed using mixed-effects regression models appropriate for the type of outcome variable, adjusting for minimisation variables and individual-level factors including age, sex, and vaccination status as fixed effects with a random effect for care home.

Ordered categorical outcomes will be analysed similarly as the primary outcome.

Continuous outcomes will be analysed using linear mixed-effect model, with further adjustment for baseline outcome measure if available. The estimated between group effect will be presented using the adjusted difference between means, along with a 95% confidence interval.

Binary variables will be analysed using mixed effects logistic regression model. The between group effect will be reported using an adjusted risk difference and adjusted risk ratio along with corresponding 95% confidence intervals, obtained using Stata's Margins command with standard errors computed using the delta method.

All-cause mortality (time to death) will be analysed using mixed-effects Cox regression model (shared frailty model). A Kaplan-Meier curve will be presented by trial arm. Other time-to-event outcomes will be analysed using competing-risks survival regression with cluster–robust standard errors. The between group effect will be reported using an adjusted hazard ratio along with a corresponding 95% confidence interval. Estimated cumulative incidence function graphs will be presented for each of the outcomes by trial arm.

The care home level infection rate outcome will be analysed using multiple linear regression of the cluster proportions, adjusted for the cluster-level minimisation variables, to obtain the adjusted difference in mean rates between the intervention and control arms along with the corresponding 95% CI. Poisson regression on cluster-level rates, adjusted for the cluster-level minimisation variables, will be used to obtain estimated rate ratio with corresponding 95% CI. The regression models will be weighted by the inverse of the variance of each cluster summary to take account of variability in cluster size. For this outcome, there will be no adjustment for individual-level covariates since not all residents will have individual level infection data to allow for individual-level analysis.

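### SAP Table 1 makes COVID-19 death and cause-specific admission descriptive only, contradicting SAP 7.4, Protocol 13.2 and the stated objective, with no departure recorded

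*SAP*

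**What the plan says.** The secondary objective in both synopses is "To assess the effects of trial treatments on mortality (all-cause and cause-specific), admission to hospital (all-cause and cause-specific" (SAP 2).

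Two general rules say how such outcomes are analysed. Protocol 13.2: "Secondary outcomes will be analysed using appropriate regression models dependent on data type (binary, categorical, continuous, time to event etc.), adjusted similarly", with clustering taken into account. SAP 7.4: "Individual-level secondary outcomes will be analysed using mixed-effects regression models appropriate for the type of outcome variable". For binary outcomes SAP 7.4 is explicit: "Binary variables will be analysed using mixed effects logistic regression model", and "The between group effect will be reported using an adjusted risk difference and adjusted risk ratio along with corresponding 95% confidence intervals".

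SAP Table 1 (section 2.4) then sets the method outcome by outcome. In the row "Cause-specific mortality, including COVID-19, stroke, pulmonary embolism, myocardial infarction", each of the four causes is typed binary and given the method descriptive. The row "Cause specific hospital admission" also has the method descriptive; its description and data type are blank and no causes are listed.

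Death and admission are modelled only as all-cause outcomes: the ordinal outcomes, time to first admission, days alive and out of hospital, and time to death ("All-cause mortality (time to death) will be analysed using mixed-effects Cox regression model (shared frailty model"). The changes-from-protocol table at the front of the SAP shows no entry.

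**The concern.** The SAP gives two answers for COVID-19 death. Section 7.4 leads to an adjusted risk difference and risk ratio with intervals; Table 1 leads to counts by arm. An analyst following Table 1 would leave part of a stated objective without an estimate, and the departure from Protocol 13.2 would be unrecorded.

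Levels 3 and 4 of the primary outcome are all-cause. Protocol 9.2.1 lists events that are frequent in care homes, among them falls with fracture, sepsis, urinary infection and heart failure, and says that they count towards the primary outcome if they lead to hospitalisation or death. If the all-cause results are null or modest, readers will ask whether severe COVID-19 was unaffected or whether an effect was diluted. Raw counts cannot be read safely for this in a trial that plans on a design effect of 5.25. The milder COVID-19 outcomes get models and the two most serious do not, and the SAP gives no reason.

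**Working it through.** **1. The texts side by side**

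| Source | COVID-19 death | Cause-specific admission |
|---|---|---|
| Secondary objective | assess the effect | assess the effect |
| Protocol 13.2 | adjusted regression, clustering allowed for | same |
| SAP 7.4, general rule | mixed-effects regression | same |
| SAP 7.4, binary rule | mixed logistic; risk difference and ratio with 95% CI | not clearly covered, as data type is blank |
| SAP Table 1 | binary; descriptive | type blank; descriptive |
| Changes-from-protocol table | no entry | no entry |

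The cause-specific deaths are the only rows that Table 1 types as binary. If Table 1 governs, the binary rule in 7.4 has no listed outcome to apply to.

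**2. The plan's own figures (SAP 2.1)**

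Design effect = 1 + [(CV² + 1)m − 1] × ICC = 1 + [(0.49² + 1) × 32 − 1] × 0.11 = 5.255, stated as 5.25. Homes = 2 × 530 × 5.25 / 32 = 173.9, stated as 174 and raised to 200. Both reproduce, and the sample size is not at issue. With 3,200 residents per arm, the effective n per arm is 3,200 / 5.25 ≈ 610.

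**3. Illustration: COVID-19 death against all-cause death**

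From the plan: 15% all-cause mortality in standard care and a design effect of 5.25, here applied to both outcomes. Assumed, because the documents do not give them: the COVID-19 share of deaths, and a treatment that reduces only COVID-19 deaths.

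z = |p − q| / √{[p(1 − p) + q(1 − q)] / 610}; power = Φ(z − 1.96).

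For a share of one half and a risk ratio of 0.67:
- COVID-19 death, 7.5% against 5.025%: z = 0.02475 / 0.01386 = 1.79, power 43%.
- All-cause death, 15% against 12.525% (risk ratio 0.835): z = 0.02475 / 0.01972 = 1.25, power 24%.

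For a share of one half and a risk ratio of 0.5:
- COVID-19 death, 7.5% against 3.75%: z = 2.85, power 81%.
- All-cause death, 15% against 11.25%: z = 1.94, power 49%.

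| Risk ratio for COVID-19 death | COVID-19 share | Power, COVID-19 death | Power, all-cause death |
|---|---|---|---|
| 0.67 | 25% | 24% | 9% |
| 0.67 | 50% | 43% | 24% |
| 0.67 | 75% | 60% | 48% |
| 0.5 | 30% | 59% | 21% |
| 0.5 | 50% | 81% | 49% |
| 0.5 | 70% | 93% | 80% |

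**4. What an interval adds to counts**

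SE(log RR) = √[(1 − p)/(np) + (1 − q)/(nq)], with n = 3,200 / design effect and q from an odds ratio of 0.67. The control risks of COVID-19 death are assumed.

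| Control risk | Events, both arms | RR | 95% CI, design effect 5.25 | 95% CI, clustering ignored |
|---|---|---|---|---|
| 10% | 542 | 0.69 | 0.48–1.01 | 0.59–0.82 |
| 5% | 269 | 0.68 | 0.39–1.18 | 0.54–0.86 |
| 2% | 107 | 0.67 | 0.28–1.62 | 0.46–0.99 |

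There are enough events to fit a model across this range. A reader who put a simple interval on the published counts would exclude 1 in all three rows; with the plan's design effect, none does.

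No figure is given for COVID-19 admission. The plan's 10% is the proportion whose worst event is admission, not the admission risk, and no COVID-19 share is stated.

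**The case against.** **Section 7.4 already asks for the estimate.** A reader might infer that the trial will give no treatment effect for COVID-19 death. The documents do not settle that. As written, 7.4 and Protocol 13.2 call for one, and Table 1 conflicts with them. The SAP's dummy tables, which might show the intention, are not in the public text. For admission, COVID-19 is not named as a cause, so that outcome is covered only by the general rules. This objection stands: the defect is an unresolved contradiction, and the loss follows only if Table 1 is followed.

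**COVID-specific effects are modelled elsewhere.** It would be wrong to infer that the plan leaves the COVID-19 pathway unanalysed. Time to infection, healthcare referral, oxygen and dexamethasone use for COVID-19 have competing-risks models, and the care-home infection rate has its own regression. This stands too, but none of these is death or admission.

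**All-cause endpoints have reasons.** Protocol 1.2 reports that residents without direct evidence of infection were twice as likely to die if their home had an outbreak. Protocol 1.1 links COVID-19 to stroke, pulmonary embolism and myocardial infarction, and Protocol 1.2.4 to later deconditioning. Deaths not labelled COVID-19 may therefore be preventable. Staff are unblinded and testing follows each home's routine, so labelling could differ by arm, and register data do not remove bias that arises before registration. These are good reasons to keep all-cause outcomes primary. They do not justify leaving a listed secondary outcome without an interval.

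**Power may be low.** At an effect near the planned odds ratio, a model would often be inconclusive. That is true, but the wide interval is itself the information that counts conceal, and SAP 7 already treats secondary outcomes as supportive.

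**Conclusion.** The point holds as a contradiction within the SAP, and as an unrecorded departure from Protocol 13.2 if Table 1 governs. In that case the trial reports no cluster-adjusted effect for COVID-19 death or COVID-19 admission, which leaves part of a stated secondary objective unanswered. It should be corrected, but it does not threaten the primary analysis or the sample size.

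The gain from modelling depends on figures that the documents lack. With half of deaths due to COVID-19, power for COVID-19 death against all-cause death is about 43% against 24% at a risk ratio of 0.67, and 81% against 49% at 0.5. The higher pair assumes a larger effect than the planned odds ratio of 0.67 and should not be read as the expected performance. All these figures assume correct attribution of cause, no effect on other deaths, and the primary outcome's design effect. Under those assumptions COVID-19 death is the more informative outcome in every scenario tabulated; misattribution, or benefit on other deaths, would narrow or reverse the difference.

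**What to change.** - **COVID-19 death, Table 1.** Replace descriptive with a modelled estimate and 95% CI. The simplest choice is the mixed logistic model that 7.4 already prescribes, with adjusted risk difference and risk ratio. The alternative is the competing-risks regression with cluster-robust standard errors used elsewhere in the table, with other-cause death competing; the data type must then become time-to-event.
- **COVID-19 admission, Table 1.** Name COVID-19 as a cause within the admission row, give it a data type, and analyse it in the same way as COVID-19 death, in the set used for time to first admission (which excludes residents with a directive against hospitalisation).
- **SAP 7.4.** State that stroke, pulmonary embolism, myocardial infarction and other causes stay descriptive because events will be few, and enter this in the changes-from-protocol table.
- **Attribution and status.** Take cause from the routine registers, the only outcome source described as blinded. Keep the all-cause outcomes primary and the cause-specific estimates supportive, and state the risk of differential labelling.

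If the sponsor prefers counts only, that choice should be recorded and justified as a departure, and 7.4 amended to match.

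The cost is a few Table 1 cells, a short addition to 7.4, one log entry and two more models per comparison. The hospital and mortality data are already to be linked (Protocol 10.3). The change should be made before allocations are released for the comparison. The downside is less certain attribution than for all-cause events, which the supportive status addresses.
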